## Randomization

Due to the community-based nature of the approach (i.e., implemented at the level of the zone) and integration of the CCDT into routine practice, randomization takes place at the zone level.

Data is therefore collected per zone, instead of on the individual child, adolescent or caregiver level. Each zone will be randomized to a sequence and start timing for when the CCDT will be introduced there using a random number generator in Stata, Version 17. Randomization will be done by the lead statistician based in the USA.

## **Intervention: Community Case Detection Tool**

The Community Case Detection Tool (CCDT), is a tool for trusted and respected community members, without a professional mental health background, that supports proactive identification of children and adolescents in need of mental healthcare services to encourage help-seeking at available adequate mental health services. The CCDT capitalises on people's almost universal skill to easily recognise overall patterns of behaviour in others. The CCDT is made up of illustrated narratives depicting common examples of childhood psychological distress, such as social withdrawal, school refusal, aggression, sleep problems, unexplained physical illness and injuries, and loss of hope. See Annex 1 for an example of the CCDT, developed in Sri Lanka. Each narrative is based on specific cultural idioms of distress to allow for simple identification. We are currently adapting the tool to the Ugandan context through input from local key stakeholders and service providers. It will be available in most common languages spoken in the five settlements, including Kiswahili, Kinyamwisha, Juba Arabic, Lugbara, Kakwa and Kuku.

The narratives avoid using any stigmatising or psychiatric terminology and are phrased in simple, familiar language. The illustrations make the tool even more accessible to people with different literacy levels. These narratives are paired with a simple decision diagram - which allows community gatekeepers to determine the level of match and advise on follow-up actions.

When a child matches the patterns of behaviour presented through the tool, the community gatekeeper will encourage help-seeking and hand out a referral card with information about TPO. If they decide to seek help, TPO's clinical team will conduct a formal assessment and provide care or they refer the child and caregiver to other available services, depending on their needs. Children and adolescents in need of urgent support will be directly referred to a mental health professional.

#### **Control Condition**

In the control condition (i.e., zones pre-introduction of the CCDT), practice-as-usual with regards to identification and referral takes place until the CCDT in introduced. Practice-as-usual consists of awareness raising activities organized by TPO. This happens through psycho-education group

sessions, home visits, radio talk shows and community dialogue sessions. These methods are used as community entry strategy, to provide information about mental health services, to assess broad mental health needs in the community and provide therapy or medication follow up. As a result, caregivers will refer themselves, or the volunteer psychosocial assistants or social workers identify children and adolescents in need of care.

Any changes in identification methods during the implementation of this study will be reported to the research team.

## **Procedures**

## Training and supervision of clinical team

All members of the clinical team will be trained on the protocol, using the case register forms, informed consent/assent, ethical principles, child safeguarding, reporting and managing adverse events, and data management. The training will be conducted by the research team, and will be a two-day training. Since this study is embedded in routine practices, the clinical team will already be trained by TPO in their clinical procedures and treatment but a one day of refresher training will be organized by TPO for the clinical team.

## Training and supervision of program team

The project officers involved in data collection and management will be trained in the protocol, study procedures and informed consent/assent, ethical principles, data collection and management, child safeguarding and reporting and managing adverse events. The training will be conducted by the research team, and will be a two-day training. The co-investigator/research coordinator will oversee ethical conduct, data collection and data management and will arrange monthly meetings with the clinical and program team involved in data collection and management.

# Training and supervision community gatekeepers

The research team will arrange a two-day training of trainers in using the CCDT for TPO's clinical psychologists and WCH's psychosocial support project officers before the start of the study. Gatekeepers attached to the same zone will be trained in the week prior to the transition step. This will be a two-day training in using the CCDT and help-seeking promotion and will be conducted by one of TPO's clinical psychologist and one of WCH's psychosocial support project officers working in the same zone/settlement. The training will be conducted in English and their local language and involves multiple interactive discussions, case studies and role-plays and will address the following topics:

- Responsibilities and child safeguarding
- Basic information about the topic of child and adolescent mental health
- Detection tool and identification procedure per version
- Ethical issues associated with proactive case-finding
- Basic training on consent to gather information
- Stressing that referral to in-depth assessment is encouraged, but never imposed

All gatekeepers will conduct several simulation sessions of the use of the tool, in order to develop their skills and to allow the research and program team to detect any problems with implementation.

The community gatekeepers will be linked to one clinical psychologist who will offer ongoing support and supervision. During the first two months, the supervision sessions will be bi-weekly, after that a monthly supervision meeting will be organized at the end of every month. These sessions will be led by a clinical psychologist and supported by one psychosocial support project officer. The purpose of these sessions is to support the gatekeepers' wellbeing, to oversee the quality of their work and to discuss challenges and possible ways to overcome them.

#### Local Permissions and authorization

Local permissions to approach communities and support to conduct this study will be sought from community and district officials in the study areas, prior to commencing the trial.

#### Informed Consent and Assent procedure

Consent and assent will be sought from caregivers, children and adolescents that seek help, and from community gatekeepers:

## Caregivers, children and adolescents

Informed consent/assent will be obtained at two levels:

• By gatekeepers, at community level upon detection: This study will be integrated in routine practices and community gatekeepers will engage caregivers, children and adolescents as they would usually do in routine practice. They visit the family and provide information about TPO's services and encourage help-seeking. At this stage, there is no engagement in any study activity yet, however some information will be collected for study purposes. Gatekeepers will therefore provide a verbal summary of the project to caregivers, adolescents and children upon detection and help-seeking encouragement (see Annex 3.2). After providing this information, gatekeepers will ask verbal consent/assent to document and release their

information to the study team for study purposes. Information will only be documented if both the caregiver and child/adolescent give their verbal consent. Caregivers, or children/adolescents that do not consent to the sharing of data will not be included in the study, but will continue to be involved in any service delivery they need—if they desire to make use of these services. If a child/adolescent is detected but there is no caregiver available, they will be provided similar information regarding help-seeking but their data will not be used. For caregivers, adolescents and children that consented, gatekeepers will record the date of verbal consent and document the child's and family name, contact details, age, version of the CCDT used and if it concerns a new or an old detection in their logbook.

• By clinical team, at service level, upon entry to care: consent will be sought from caregivers/parents of children below 17 years and adolescents, and assent form for children between 6 to 17 years, that seek help at TPO. The clinical team will provide information about the study and ask for consent to document and release their de-identified information with WCH for study purposes (see Annex 3.3 and 3.4). Caregivers, or children/adolescents that do not consent to the sharing of data will not be included in the study, but will continue to be involved in any service delivery at any time. Since it concerns routinely collected data, their family name, age and phone number is needed in order to delete their information and exclude it from analysis.

Community gatekeepers: verbal and written informed consent will be obtained before participating in this study. They will first be given written information about the program and their role in their local language. This information will be handed out by the project officer engaged in selecting the gatekeepers (see Annex 3.1). For community gatekeepers that consented, the project officer will record the gatekeepers' name, age and level of education, occupation and role in the community.

All completed consent documents will temporarily be retained at TPO's field offices for monthly collection by the research team. All participants (community gatekeepers and caregivers) will be given the name and number of the study contact person in Uganda in case they have further questions, or wish to withdraw from the study. All participants will have the right to withdraw from the study and without obligation to provide a reason.

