## Research questions

- Can proactive community case detection using the CCDT increase utilization of TPO's mental healthcare services among children and adolescents in the Bidi Bidi, Rhino, Omugo, Kyaka II, and Kyangwali settlements in Uganda?
- 2. What is the proportion of children and adolescents who seek mental health care as a result of having been detected using the CCDT?
- 3. Is proactive community case detection using the CCDT acceptable, appropriate, and feasible to implement at scale in the Bidi Bidi, Rhino, Omugo, Kyaka II, and Kyangwali settlements in Uganda?
- 4. How do community gatekeepers' attitudes towards individuals experiencing mental health problems relate to the implementation of the CCDT in the Bidi Bidi, Rhino and Omugo, Kyaka II, and Kyangwali settlements in Uganda?

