## Specific inclusion criteria are:

- At least 18 years of age;
- Trusted and respected members from the community;
- Engaged in promoting child wellbeing;
- Access to children, adolescents and caregivers;
- Demonstrate high level of empathy and interest in children's wellbeing;
- Willing to provide informed consent and participate in supervision meetings to provide feedback on feasibility of the approach;
- Willing to sign and follow WCH's Child Safeguarding Policy, Code of Conduct and Code of Ethical conduct in using the CCDT.

Community gatekeepers will be invited for a two-day training and monthly supervision and debrief meetings (for the duration of CCDT implementation in each of the zones) as part of this project. During the first two months, the supervision sessions will be bi-weekly, after that it will continue on a monthly basis. Consent will be sought for their participation in the project as community gatekeepers and for their participation in the nested qualitative study to capture their feedback on the implementation outcomes (see Annex 4.3). Following usual practices within WCH and TPO's current work, active gatekeepers will be provided transportation and lunch when called for the meeting. They will also be provided airtime to follow up and report on the cases. Regular monthly incentive is not planned under this project. Community gatekeepers from the same zone will be linked to TPO's clinical team serving their zone.

Children, Adolescents, and their Caregivers

Children, adolescents aged 6-18 years old, and their caregivers will be proactively identified by the trained community gatekeepers based on a match with the CCDT (i.e., children and adolescents in need of mental healthcare services). Whenever a trained gatekeeper encounters a child or adolescent that matches with the tool, they will hand out a referral card for TPO and encourage help-seeking at TPO's clinical team serving their zone. Consent procedures are described in the following sections and in Annex 3.

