# **Outcome measures**

#### Primary outcome measure

The primary outcome is utilization of TPO's mental healthcare services among children and adolescents detected by the CCDT. Utilization in this study will be defined as initial encounters with TPO's mental healthcare among children and adolescents 6-18 years old or their caregivers, or re-entry into services for children and adolescents that have not been using TPO's services for 6 months. This is measured in two ways:

(1) Service utilization data: the number of children and or adolescents aged 6-18 years old that seek mental healthcare services from TPO, compared to utilization rates of practice-as-usual (i.e., during the pre-CCDT period). TPO's routinely collected monthly mental health service utilization data will be used for this. Following routine practices, upon intake, TPO's clinical team completes a 'case registration form' (see Annex 4.1).

- (2) The proportion of children and adolescents detected by the CCDT as in need of mental healthcare that seeks help at TPO. Two data sources will be used and compared for this:
  - a. Detection data: number of detected cases per gatekeeper. Gatekeepers will be trained in keeping a log of the number of detected children while using the CCDT (see Annex 4.2). Gatekeeper logbooks will be collected bi-weekly by one of WCH's facilitators attached to the zone and handed over the project officers who will be trained in entering the data in a digital master sheet.
  - b. Service utilization data: Number of cases contacting TPO as a result of a community gatekeeper trained in the CCDT handing out a referral card. The same 'monthly mental health service utilization data' (see outcome 1 above) will be used for this. TPO's clinical team will be trained to ask all new clients (children, adolescents or caregivers) an intake question regarding the reason for seeking help (including the community gatekeeper handing out the referral card as one of the options). This data is entered by the clinical psychologist in the 'case registration form' used upon entry.

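### The help-seeking proportion draws its numerator and denominator through different, unlinked consent filters, so its bias has no known direction and it is not bounded by 100%

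*Protocol*

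**What the plan says.** The target is research question 2: "What is the proportion of children and adolescents who seek mental health care as a result of having been detected using the CCDT". The same quantity is secondary objective 1. It is listed as the second measure under Primary outcome measure and again as a secondary outcome in the Statistical Analysis plan section.

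- **Cards.** Under Participant Recruitment and Eligibility Criteria, when a child matches the tool, gatekeepers act at once: "they will hand out a referral card for TPO and encourage help-seeking at TPO's clinical team serving their zone". The Intervention section says the same. Neither makes the card depend on consent.
- **Denominator.** Primary outcome measure, item (2)a: "Detection data: number of detected cases per gatekeeper", with the explanation "Gatekeepers will be trained in keeping a log of the number of detected children while using the CCDT".
- **Limits on the log.** Informed Consent and Assent procedure, at community level: "Information will only be documented if both the caregiver and child/adolescent give their verbal consent". A further limit follows: "If a child/adolescent is detected but there is no caregiver available", the child is still told about help-seeking but the data are not used.
- **Numerator.** Primary outcome measure, item (2)b: "Number of cases contacting TPO as a result of a community gatekeeper trained in the CCDT handing out a referral card". It comes from one intake question on the case registration form. Consent to release data is sought separately at entry to care, and the records of those who decline are deleted and excluded from analysis.
- **Linkage.** Description of data collected gives the log a study ID said not to be traceable to the individual, and gives TPO clients a code of their own as sole identifier. The data-flow section for detection data has only the number of detected cases entered in the master sheet.

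**The concern.** The Statistical Analysis plan section describes the result as the detected children who used TPO's care, that is, a subset of those detected. The data flow does not deliver a subset. One consent filter acts on the denominator in the community, another acts on the numerator at the clinic, and nothing ties an intake record to a log entry. A family that declined to be logged can still hold a card, come to TPO, agree to release data there and be counted above the line without ever having been counted below it.

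At stake is the whole quantitative answer to research question 2. Part of the gap cannot be closed at the analysis stage. Unlogged detections leave no record, so neither the logging rate nor the difference between logged and unlogged children can be estimated later.

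**Working it through.** **Stated figure.** The protocol gives no expected value for this proportion, no logging rate and no release-consent rate, so there is nothing to reproduce. The sample-size inputs do not enter this point.

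**Inputs**
- c: share of detections that are logged (both consents given, caregiver available). Not in the documents; assumed.
- s: share of arriving card-holders who consent to release at TPO. Not in the documents; assumed.
- h: true share of detected children who seek care. Illustrated with 67%, which the Rationale and background section cites from earlier work with the adult tool in Nepal. It is not a planning value for this trial.

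**Formula.** Use subscripts L for logged and U for unlogged children. Per detected child, the counted numerator is c·h_L·s_L + (1 − c)·h_U·s_U and the denominator is c, so

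reported = [c·h_L·s_L + (1 − c)·h_U·s_U] / c, while true = c·h_L + (1 − c)·h_U.

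If both groups behave alike, this reduces to reported = h × s/c. It is too high when s > c, too low when s < c and correct when s = c.

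**Equal behaviour, h = 0.67**

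| c | s | reported |
|---|---|---|
| 1.0 | 0.8 | 0.67 × 0.8/1.0 = 53.6% |
| 0.9 | 0.8 | 0.67 × 0.8/0.9 = 59.6% |
| 0.8 | 0.8 | 0.67 × 0.8/0.8 = 67.0% |
| 0.8 | 0.9 | 0.67 × 0.9/0.8 = 75.4% |
| 0.8 | 1.0 | 0.67 × 1.0/0.8 = 83.8% |

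The multiplier s/c does not depend on h. With c and s both between 0.8 and 1 it runs from 0.8/1 = 0.80 to 1/0.8 = 1.25. A true 30% would then read between 24% and 37.5%.

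**Bound.** The ratio exceeds 100% when c < h × s.
- At h = 0.67: c below 0.67 (s = 1), 0.603 (s = 0.9) or 0.536 (s = 0.8).
- At h = 0.30: c below 0.30, 0.27 or 0.24.

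**Unequal behaviour, c = 0.8 and h_L = 0.67**
- Unlogged children seek care equally often but all decline release at TPO, with s_L = 0.9: (0.8 × 0.67 × 0.9)/0.8 = 60.3%, against a true 67%. Too low.
- Unlogged children seek care half as often (0.335) and everyone consents at TPO: (0.8 × 0.67 + 0.2 × 0.335)/0.8 = 75.4%, against a true 60.3%. Too high.

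**With linkage.** If the numerator counts only logged children matched to a TPO record, reported = h_L × s_L, which cannot exceed 100%. At h_L = 0.67 it is 67% for s_L = 1 and 60.3% for s_L = 0.9. What remains is under-counting from refusals at TPO, which can be reported.

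**The case against.** A reader might infer that the proportion is inflated, on the view that every card-holder reaching TPO is counted over a denominator shorn of refusers. The documents do not support that. TPO seeks its own consent, by signed release form where detection needs only verbal agreement, and deletes those who decline. The clinic filter may be the stricter one, and then the figure is too low. That families who refuse logging are less willing to seek help is plausible but is an assumption. A figure above 100% is possible but needs a low logging rate, as shown above; it is not to be expected.

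Other points on that side:
- **Matching may be feasible.** Logbooks hold names and contact details and pass to TPO's clinical psychologists, a master list links IDs to names, and an analysis plan not shown could set out matching. This stands in part: matching could make the numerator a subset. But no such use is described, and matching cannot recover detections that were never written down.
- **Children without a caregiver.** The sentence about them does not mention a card, and TPO also seeks caregiver consent for younger children. This narrows one route into the numerator. It does not close the route for families who declined logging.
- **No true contradiction.** The outcome section may state the log's purpose and the consent section a condition on its entries. They can be read together, but then detected means logged with consent, which the outcome definition does not say.
- **Limited reach.** The proportion is analysed descriptively. The rate ratio uses TPO counts and a child-population offset, not the log, so this point leaves it untouched.

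**Conclusion.** The concern holds as a mismatch between numerator and denominator, with bias of unknown direction. As the data flow is written, the numerator is not a subset of the denominator, contrary to the wording of the Statistical Analysis plan section, and the ratio has no upper bound of 100%. For an illustrative true value of 67%, logging and release-consent rates each between 0.8 and 1 give a reported value from about 54% to 84%. Those rates are assumptions, and the range also assumes that logged and unlogged children behave alike. The protocol collects nothing that would let a reader place the truth within that range. A claim of inflation, or of a value above 100%, would go beyond the documents.

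**What to change.** 1. Have gatekeepers keep an anonymous tally of every card issued, marked logged, refused or no caregiver, with no personal data. Report the number of cards issued and the logging rate.
2. Define the main proportion among logged, consenting children linked to their TPO record, using a card number written in the log and at intake for consenting families only. The number must not make refusers identifiable.
3. Report the release-consent rate at TPO beside the proportion.
4. Reconcile the log as described under Primary outcome measure, the consent condition under Informed Consent and Assent procedure, and the subset wording in the Statistical Analysis plan section.

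The cost is a small addition to the logbook and one field on the case registration form. The tally needs ethics-committee agreement because it marks refusals, even without personal data. The resulting figure may be less favourable.

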#### DATA COLLECTION AND PROCESSING

#### Description of data collected

Both quantitative and qualitative data will be collected.

Quantitative data

Quantitative data will be collected at two levels:

- 1) Detection data Gatekeepers will be provided with a logbook in which they will record the information about the detection (see Annex 4.2). A unique study ID will be created for each new case, this code will be linked to the gatekeepers' initials and cannot be traced back to the individual. The following information will be collected by gatekeepers:
  - o Study ID
  - Child's demographic information: age, gender, status (refugee/host), village, zone and settlement of residence
  - Contact details family
- Version of the CCDT used (i.e., the CCDT vignette that matched their observations)
- o Date of detection and engagement
- Date of verbal consent/assent obtained

This data will be collected in the zones where the CCDT is introduced, from the moment that the gatekeepers start using the CCDT, until the end of the project duration (i.e., April, 2023).

- 2) Service utilization (TPO) routine data will be collected at TPO for all clients seeking care. An anonymized client code will be assigned and used as the only identifier. The following variables will be collected in the Case Registration Form (see Annex 4.1):
  - Client ID
  - Demographic information: age, gender, status (refugee/host), village, zone and settlement of residence
  - Referral type: through CCDT or routine
    - This will be obtained through the referral card handed out by the gatekeeper using the CCDT (i.e., 'someone in the community approached me, handed out a referral card and encouraged me to seek help here')
  - Date of intake
  - Type of visit: new, re-entry or recurring/maintenance visit.
  - Mental health diagnosis
  - Service or type of treatment provided by TPO, or referral made

If treatment was initiated and completed.

This data will be collected from the beginning of the study in all zones, until the end of the project duration (i.e., April, 2023). A study specific data extraction sheet will be developed which will be used to collect all the information according to the primary and secondary outcomes.

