## Description of quantitative data flow and entry system

The different forms of data will follow a different data flow and entry system as described below:

Detection data (gatekeeper logbook)

Figure 2 Data flow: Detection

Gatekeeper logbooks will be collected every two weeks by zone facilitator/psychosocial volunteers linked to that zone, and handed over to the clinical psychologists at TPO. The paper versions will be stored in a secure lockable cabinet at TPO's field office. A two-week timeframe is selected to allow for quality monitoring and follow up.

TPO's M&E Manager will enter the number of cases detected in a master excel sheet, stored on a password encrypted secure data server of the R&D Department of WCH.

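### The help-seeking proportion sets TPO card-holders against consented logbook detections under different consent filters with no described link, so it is not a proper proportion and its bias has unknown direction

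*Protocol*

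**What the plan says.** The proportion answers research question 2 and secondary objective 1. The Outcome measures section lists it as the second component of the primary outcome, and the Statistical Analysis plan section lists it again among the secondary outcomes. That section describes it as a descriptive within-group analysis: of the children detected with the CCDT, how many went on to use TPO care over the whole project.

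- **Denominator** (Primary outcome measure, 2a): "Detection data: number of detected cases per gatekeeper", taken from the logbooks.
- **Numerator** (Primary outcome measure, 2b): "Number of cases contacting TPO as a result of a community gatekeeper trained in the CCDT handing out a referral card". New clients are identified by an "intake question regarding the reason for seeking help (including the community gatekeeper handing out the referral card as one of the options").
- **Who receives a card** (Participant Recruitment and Eligibility Criteria): "Whenever a trained gatekeeper encounters a child or adolescent that matches with the tool, they will hand out a referral card for TPO". Consent to data collection is not a condition.
- **Who is logged** (Informed Consent and Assent procedure, community level): "Information will only be documented if both the caregiver and child/adolescent give their verbal consent". For a child detected with no caregiver available, "they will be provided similar information regarding help-seeking but their data will not be used".
- **Who is retained at TPO** (same section, service level): a second, separate consent is sought on entry to care. The records of those who refuse are deleted and left out of the analysis.
- **Identifiers** (Description of data collected): the logbook carries a Study ID, described as not traceable to the individual. For TPO data, "An anonymized client code will be assigned and used as the only identifier". The Study ID is not among the variables listed for the case registration form.
- **Data entry** (Description of quantitative data flow and entry system): "TPO's M&E Manager will enter the number of cases detected in a master excel sheet". The Primary outcome measure section instead has project officers entering the logbook data in a digital master sheet.

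**The concern.** A within-group proportion requires every numerator case to be in the denominator. Here two routes break that, and they pull in opposite directions.

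1. A matched child who is not logged, because consent was refused or no caregiver was there, still receives the card or the help-seeking information. If that child later attends and consents at TPO, the child counts in the numerator only.
2. A logged child who attends but whose family refuses release at TPO is removed from the numerator and stays in the denominator as an apparent non-attender.

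The reported figure would then move with caregiver availability and with consent at two separate points, as well as with help-seeking. Research question 2 would be answered by a number that cannot be read as the share of detected children who sought care. A later analysis plan could not repair this if the linking identifier was never recorded at intake.

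**Working it through.** The protocol gives no expected value, target or precision for this proportion, so there is no figure to reproduce. The 28-zone power calculation concerns the utilization rate and does not bear on it.

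**Notation**
- c = share of detections that are logged (the detection consent rate, including loss through caregiver absence)
- p1, p0 = help-seeking among logged and unlogged detections
- q1, q0 = TPO consent rate among attenders in those two groups

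**Inputs.** The documents give none of c, q1 or q0. Assumed ranges are c = 0.60 to 0.95 and q = 0.70 to 1.00. For scale only, p = 0.67 is the share of detected cases who went on to access care in the Nepal work with the adult tool, cited in the Rationale section.

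**Formulas**
- Reported ratio: R = [c·p1·q1 + (1−c)·p0·q0] / c = p1·q1 + ((1−c)/c)·p0·q0
- True proportion over all detected: T = c·p1 + (1−c)·p0
- If q1 = q0 = q: R = T·q/c. R exceeds T when q > c, equals it when q = c, and falls below it when q < c.
- If also p1 = p0, T is the proportion in logged children as well.

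**Results with p1 = p0 = 0.67, so T = 0.67**

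| TPO consent q | Logged share c | R = 0.67·q/c | Error |
|---|---|---|---|
| 1.0 | 0.6 | 1.117 | +0.447 |
| 1.0 | 0.8 | 0.838 | +0.168 |
| 1.0 | 0.9 | 0.744 | +0.074 |
| 0.8 | 0.8 | 0.670 | 0 |
| 0.8 | 0.9 | 0.596 | −0.074 |
| 0.7 | 0.95 | 0.494 | −0.176 |

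The first and last rows are the extremes over the assumed ranges.

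**When the ratio exceeds 100%.** This needs T·q > c. At T = 0.67 and complete TPO consent, c must be below 0.67.

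**Unequal TPO consent.** Families who declined at detection may decline again. With c = 0.8, p1 = p0 = 0.67 and q1 = 0.9:
- q0 = 0.5: R = 0.67 × 0.9 + (0.2/0.8) × 0.67 × 0.5 = 0.603 + 0.084 = 0.687
- q0 = 0: R = 0.603, below the true 0.670

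**After linkage.** With only logged cases in the numerator, R = p1·q1, which cannot exceed 1. At p1 = 0.67 it is 0.670, 0.603 and 0.536 for q1 = 1.0, 0.9 and 0.8. The excess numerator cases are gone; the loss through TPO refusal remains.

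**The case against.** A reader might infer that the proportion is biased upward, by a factor of one over the share logged. The documents do not support that. The factor holds only if every attender consents at TPO, and the same consent section deletes those who refuse there. The sign turns on two rates that the protocol does not give.

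The consent section can also be read as excluding unconsented children from both sources, since it says that they are not included in the study and does not limit this to the logbook. That reading is fair, but no means is described by which TPO would recognise a child who was never logged.

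Linkage may be possible. The logbook holds names and contact details, a master list links IDs to names, and the Monitoring section has clinical psychologists checking that referred children are captured and correctly coded. The account of data entry is also inconsistent, so it is not established that only counts reach the central file. All of this stands as evidence that matching could be done; none of it says that matching is planned for this proportion.

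The intended target, in Table 1 and the Statistical Analysis plan section, is clearly a subset of detected children, and the joining of records might be set out in forms or a plan not shown. The absence of the Study ID is read from the protocol's list of form variables. But whether the ID is captured at intake is a matter of data collection, which an analysis plan cannot supply afterwards.

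Finally, this is a descriptive proportion with no test attached, which limits the consequence.

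**Conclusion.** The point holds in this form: as written, numerator and denominator pass through different consent filters and are not stated to be linked. The ratio is therefore not a proper proportion; its bias has unknown direction and it could exceed 100%.

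On the assumed ranges, with a true 0.67 and with equal help-seeking and equal TPO consent in logged and unlogged children, the error runs from about −0.18 to +0.45. The upper extreme needs only 60% of detections logged together with complete consent at TPO. These figures show sensitivity; they are not estimates.

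The stepped-wedge incidence rate ratio for utilization does not use the logbook denominator and is not affected. The change should be made because the proportion is the whole answer to research question 2, but it does not threaten the main comparison.

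**What to change.** 1. For consented, logged detections, write the logbook Study ID on the referral card and record it on the case registration form at intake.
2. Define the proportion as logged detections with a matching TPO intake, divided by all logged detections.
3. Report card-holders without a matching ID as a separate count, outside the proportion.
4. Report the number of refusals at TPO, because linkage does not correct that loss.
5. State that logbooks are entered case by case, and reconcile the two descriptions of who enters what.
6. Optionally, keep an anonymous count of unlogged detections per gatekeeper. This must first be reconciled with the rule that information is documented only with consent.

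Cost: one field on the card, one on the electronic form, and case-level entry. A minor ethics and consent-form update may also be needed, because a Study ID described as untraceable to the individual would now appear on the intake form.
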